3.0 Resources	
3.1 Trial site	
RMIT University Bundoora West Campus
 
[name]
 
[name]
 
Ph: [name]

3.2 Resources necessary for the project to be conducted	
Clinical testing and data collection will be performed at the RMIT Bundoora Campus Clinical Suites (Building 203). This facility includes dual-energy x-ray absorptiometry (DEXA) equipment for body composition measurements, and will be made available to the researchers by RMIT.

	
Storage and experimental analysis of collected specimens will occur at the RMIT Bundoora Campus Biosciences Laboratories (Building 223). This will include the facilitation of measurement of metabolites (metabolomics) associated with glucose, fat and protein metabolism using gas chromatography-mass spectrophotometry.
 
The laboratory/premises and equipment to be used in this research have been subjected to OHS assessments and are deemed safe for use. Relevant risk assessments will be undertaken, and standard operating procedures will be generated, prior to experimental procedures in accordance with RMIT OHS requirements.
 
Additional resources/equipment that will be used for the project include:
 
 - Blood sampling items (including syringes, needles, adhesives, cleaning swabs and blood collection tubes) - Oral glucose tolerance testing drinks - Hormone (ghrelin and insulin) kits - Gene expression analysis (including extraction chemicals, microarray kits, real-time-PCR consumables) - Gut bacteria analysis (including faecal sample collection kits, extraction chemicals, 16S rRNA profiling and metagenomics consumables) - Genetic variant testing (including buccal swabs, extraction chemical, 10 x gene variant kits and associated consumables) - Food scales - Food frequency questionnaire access - Food hampers of example food products recommended throughout the dietary intervention.

3.3 Funding support
	
Funding to the value of \$129,287.13 (AUD) has been obtained from the Allen Foundation Inc for this research project (May 31st 2018 – May 31st 2021)
 
This philanthropic grant is subject to reporting of annual progress reports (due on May 31st over the three-year funding period).

3.4 Is the research of intervention sponsored?
 
NO
 
If YES, provide details of the sponsorship and any contractual or financial agreements entered into by the researchers:
 
Not applicable
	

3.5 Are there any clinical laboratory(ies) and/or technical department(s) and/or institutions involved in the trial?
 
NO
	

4.0 Background

4.1 Does this research involve the investigation of a product (therapeutic device, drug, supplement or other type of substance)?

NO

4.2 Does this research involve the use of a physical intervention (non-device)?

NO

4.3 Does this research involve the use of a psychological, social or behavioural intervention?

YES

If YES, provide details about the intervention(s):

This project utilises two dietary interventions (behavioural), consisting of a Mediterranean diet and a general healthy eating diet (control diet). Each participant will be randomly assigned to either a Mediterranean diet (intervention) or a general healthy eating diet (control diet), for the duration of 8-weeks, followed by a cross-over (total duration 16-weeks).

Participants will receive sample meal plans, recipes and dietary advice for each dietary intervention. Nutrition advice will be provided by an Accredited Practising Dietitian ([name] and [name]). This task will be facilitated by providing nutrition education material (including sample menu plans and recipes) to each participant.

For the Mediterranean diet component, a food hamper will also be provided with relevant food items to be used during the 8-week period. Each Mediterranean meal plan will adhere to the Mediterranean diet developed in the Mediterranean Diet Model in Australia: Strategies for Translating the Traditional Mediterranean Diet into a Multicultural Setting study (George et al. 2018) and the validated protocols used in the “PREvencion con DIEta MEDiterranea” (PREDIMED) trials (Martinez-Gonzalez et al, 2012). Key features of this diet include a high plant-based (fruit, vegetables, legumes and wholegrains) and high dietary fat intake (predominantly monounsaturated fatty acids derived from extra virgin olive oil). Moderate amounts of fish, nuts and dairy are also recommended, along with red wine as being the alcoholic beverage of choice.

The general healthy eating diet will be in accordance with The Australian Guide to Healthy Eating. Food groups and portion/serve sizes will be described, with a focus on high fibre, low fat eating and reduced intake of discretionary foods.

An ad libitum approach for each diet will be advised, based on previous literature (Papamiltiadous et al. 2016; Jacka et al. 2017; Itsiopoulos et al. 2018).

Reference details listed in section 4.10

4.4 Does this research involve this use of a therapeutic device?

NO

4.5 Provide a summary of research relevant to the trial

Genetic predisposition can influence different responses to the same diet type between individuals. Therefore, personalised nutrition recommendations by health professionals, which take these differences into account, is a more suitable tool to prevent and treat nutrition-related chronic diseases than traditional “one-size-fits all” recommendations.

Nutritional genomics is a relatively new field of research assessing the mechanisms by which nutrients and dietary patterns interact with our genome at different stages. Metabolism of each nutrient involves the activity of several enzymes, each one encoded by a gene with allelic variants; each potentially contributing to the absorption and utilisation of nutrients, and ultimately influencing an individual’s nutritional requirements (Murgia & Adamski 2017). More than one allelic

variant is also generally responsible for affecting a person's predisposition to a nutrition-related disease.

Allelic variant information is not the only factor complicating the translation of nutritional genomics into nutritional practice; the discovery of other levels of control to dietary phenotyping, including the environment-modulated epigenome (e.g. microRNA activity) and the intestinal microbiome, are other complicating factors (Murgia & Adamski 2017). Although complex, all of these factors must be taken into consideration when identifying sub-groups that would benefit from particular dietary recommendations.

The Mediterranean diet is considered a dietary pattern with beneficial effects on human health, including protective effects against nutrition-related diseases (i.e. cardiovascular disease and type 2 diabetes) (Corella et al. 2013; Ros et al. 2014; Salas-Salvadó et al. 2011). The Mediterranean diet comprises an abundant consumption of olive oil, a high intake of vegetables/fruit/legumes/whole grains/nuts/seeds, and a moderate intake of red wine with meals (Fitó & Konstantinidou 2016).

High adherence to the Mediterranean diet can attenuate the incidence of stroke in carriers of the risk-T allelic variant of the Transcription Factor 7-Like 2 (TCF7L2) genes rs7903146 polymorphism (Corella et al. 2013) and negate the association between risk variants in the Fat Mass and Obesity-Associated (FTO), Melanocortin-4 Receptor (MC4R) genes and type 2 diabetes (Ortega-Azorín et al. 2012). Additionally, following a Mediterranean diet over a long-term (3 years) period resulted in the greatest body weight reduction in the obesity risk variant (AA genotype) of FTO's rs9939609 polymorphism, despite carriers of the risk variant having higher body weight than their non-risk counterparts at baseline (Razquin et al. 2010). Whilst these findings suggest a protective role of the Mediterranean diet in the link between nutrition-related diseases and their predisposing genes, further studies are necessary to determine the mechanisms involved.

Some health benefits of the Mediterranean diet have been attributed to its richness in antioxidants, which have the capacity to modulate gene and protein expression, and influence inflammation. An 8-week Mediterranean-based dietary intervention induced changes in the expression of inflammation-related microRNAs in the white blood cells of overweight subjects with metabolic syndrome (Marques-Rocha et al. 2016). Additionally, high adherence to a Mediterranean diet over 8-weeks improved metabolic syndrome features induced by weight loss, suggesting a good combined strategy to treat obesity (Hermsdorff et al. 2009). Metabolomic techniques, which allow the characterisation of a large number of metabolites present in a biological sample at one time, have also shown that an 8-week Mediterranean diet can produce significant changes to the plasma metabolic profile of individuals with metabolic syndrome (Bondia-Pons et al. 2015). Furthermore, high-level adherence of foodstuffs consistent with the Mediterranean diet has been associated with beneficial microbiome-related metabolomic profiles (De Filippis et al. 2015), with associations between gut microbiota and nutrition-related diseases, such as obesity, an emerging topic of research interest. There is a lack of evidence on how allelic variants of genes associated with nutrition-related diseases influence these outcomes.

Reference details listed in section 4.10

4.6 Provide a rationale for the trial (i.e. how the research will fill any gaps, contribute to the field of research or contribute to existing or improved practice)

The Mediterranean diet is a well-researched dietary pattern which has shown beneficial influences on health, including protective effects against metabolic diseases. However, there is limited evidence on how specific genetic variations may influence an individual's response to the Mediterranean diet on an epigenetic, gut microbiome and metabolic level. It is important to understand these factors to assist with developing dietary interventions and guidelines which are tailored to responsive individuals.

This project will provide data for several publications, each focused on genes associated with metabolic diseases. This project can provide important information on genetic sub-groups that would benefit from particular dietary recommendations, explore the possible underlying mechanisms and interactions between genes and diet, and contribute to scientific knowledge that can facilitate the translation of nutritional genomics into nutrition practice.

The findings will form the foundation for evaluating if nutritional genomic screening and personalised nutrition recommendations in healthcare settings, may be an effective strategy to treat and prevent metabolic diseases, thereby reducing the social, health and economic burden of these diseases on society.

4.7 Please describe the research question / aims / objectives /hypothesis of this project

This project is designed to determine if specific genetic sub-groups associated with metabolic disease risk benefit from a Mediterranean diet. This research may lead to personalised nutrition recommendations using genomic information to promote health.

The aims of the proposed project are to:

- (i) Determine the influence of an 8-week Mediterranean dietary intervention on gut bacteria, levels of metabolites (involved in glucose, fat and protein metabolism) present in blood, and gene modifiers (whether genes are turned on or off) in blood. This will be compared to a person’s habitual diet (baseline results) and a general healthy eating diet following The Australian Guide to Healthy Eating (control diet).
- (ii) Determine the potential of key genetic variants related to metabolic disease (including the Fat Mass and Obesity-Associated (FTO) gene, Transcription Factor 7-Like 2 (TCF7L2) gene, and Apolipoprotein E (APOE) gene) to influence gut bacteria, blood metabolite and gene modifying outcomes in response to the dietary interventions.
- (iii) Determine whether differences between genetic variants exist for body composition, key hormones (ghrelin and insulin), glucose tolerance, and dietary intake (food frequency and nutrient composition) in response to the dietary interventions.

It is hypothesized that variations in key genes associated with metabolic disease impacts on gut bacteria, blood metabolites and gene modifiers following an 8-week Mediterranean dietary intervention.

4.8 Please describe the expected outcomes of this project

Primary Outcomes:

This study will reveal if the genetic background of individuals affects their response to a Mediterranean diet by measurement of key physiological factors, including:

- Plasma metabolites associated with glucose, fat and protein metabolism
- Gene expression
- Gut bacteria diversity and composition
- Circulating hormones (ghrelin and insulin)

Secondary Outcomes:

- Body composition
- Glucose tolerance
- Food frequency and nutrient intake
- Mood state

4.9 Statement of compliance

This trial will be conducted in compliance with the Clinical Trial Protocol, the National Statement on Ethical Conduct in Human Research (2007), the Good

5.0 Project Design

5.1 Research Project Setting	The clinical sessions will be undertaken at the RMIT Bundoora Campus Clinical Suites (Building 203).
-------------------------------------	--

5.2 Trial design	The study will use a randomised, controlled, cross-over design.
-------------------------	---

5.3 Overview of the research design and theoretical approach

Please note: Specific details of the methodology (how data will be collected and analysed) is provide in sections 5.8 and 5.9.

Inclusion and exclusion criterion, and methods for participant recruitment are detailed in Section 5.4. All eligible participants will be asked to provide written consent based on RMIT approved Human Research Ethics documents. All eligible participants will be asked to read the information to participant’s form and provide written consent based on RMIT approved Human Research Ethics documents (Appendix B). Participants will be provided the opportunity to attend a familiarisation session (up to 1 hour) to discuss the study protocols and consent with the researcher.

Clinical Sessions (approximately 3 hours each):

Eligible participants will be asked to attend the Clinical Trial Suites at RMIT University Bundoora (Building 203) and asked to bring the signed consent form. Participants will be asked to complete a personal information and medical questionnaire (Appendix C).

During the initial (baseline) clinical session participants will perform a standard buccal swab (this will not be repeated in subsequent clinical sessions). Each buccal swab will be used for genetic profiling using Single Nucleotide Polymorphism arrays.

During the clinical session participants will be weighed, measured for height and have their hip to weight ratio recorded. Blood pressure will be measured using a sphygmomanometer. Participants will have their body composition measured using Dual-Energy X-ray Absorptiometry (DEXA).

Participants will then be asked to wear a respiratory mouth piece and nose clip (for approximately 10 mins) to have their respiratory gases measured every 30 seconds via an open-circuit sampling system. Respiratory data will be used to determine resting metabolic rate and each participant’s daily energy requirements. Following this, participants will perform a standard oral glucose tolerance test (OGTT) to determine glucose handling. Blood samples will be taken prior to, at 30-mins, 60-mins and 120-mins following glucose ingestion for subsequent measure.

Habitual dietary intake will be measured using a 3-day food record (2 weekdays and 1 weekend day). Participants will be asked to complete a food frequency questionnaire. Dietary quality will be assessed using the Healthy Eating Index (Basiotis et al. 2002). Mood State will be analysed using the Profile of Mood State questionnaire and the Hospital Anxiety and Depression Scale questionnaire (Appendix H (i) and H (ii)). These questionnaires will be administered whilst the participants are undertaking the OGTT. Stool samples will be collected by participants using a stool collection kit.

Following the initial (baseline) clinical session participants will be eligible to commence the dietary intervention and will be randomly assigned to either the 8-week Mediterranean dietary intervention or the 8-week General Healthy Eating intervention (Control). This dietary intervention

timeframe has demonstrated physiological changes on a molecular and metabolic level (Bondia-Pons et al. 2015; Marques-Rocha 2016).

A post intervention clinical session (as described above) will be repeated at the end point of the first 8-week dietary intervention period. The participant will then cross-over to the 8-week dietary intervention they have not yet completed. Total duration of the combined dietary intervention period will be 16 weeks. A final (third) clinical session will be repeated at week 16 (see Figure 1.0).

Dietary Intervention Mediterranean (8-weeks):

Each participant will receive a detailed sample Mediterranean meal plan, recipes, and education material to assist with adherence to a Mediterranean diet for the 8-week period. This will be explained by an Accredited Practising Dietitian. This task will be facilitated by providing a calibrated scale, a menu plan to each participant, along with a food hamper with food items that will be used as part of a Mediterranean diet.

Each Mediterranean meal plan will adhere to the Mediterranean diet developed in the Mediterranean Diet Model in Australia: Strategies for Translating the Traditional Mediterranean Diet into a Multicultural Setting study (George et al. 2018) and the validated protocols used in the PREDIMED trials (Martinez-Gonzalez et al. 2012). This includes using extra virgin olive oil (minimum 3-4 tablespoons per day), eating vegetables with every meal (100g leafy greens, 100g other vegetables, 100g tomatoes per day), at least two serves of fruit per day, legumes at least twice per week, at least three serves of fish per week, red meat less often, one serve of nuts daily, two serves of dairy daily (milk and yoghurt preferable), cheese in moderation (three days per week preferably feta, 1 serve equalling 30 grams), choice of wholegrain breads and cereals, consuming 3 eggs per week, sweets to be consumed in moderation (preferably homemade), red wine is optional (0-2 standard glasses per day, with meals, instructions to not get intoxicated). Advice on alcohol will be provided to those who already consume alcohol in their habitual diet.

Dietary Intervention General Healthy Eating (8-weeks):

Each participant will be provided with general healthy eating advice in accordance to the Australian Guide to Healthy Eating (AGTHE). This task will be facilitated by providing the participant with relevant education material, a guide to food groups and portion/serve sizes, with a focus on high fibre, low fat eating and reduced intake of discretionary foods. This diet has been chosen as a control diet based on previous literature and to also reflect current dietetic advice provided in practice to the Australian population (Papamiltiadous et al. 2016; Itsiopoulos et al. 2018).

Dietary intake will be measured using a 3-day weighed food record during the intervention mid-point (week 4) and the week before the end of each dietary intervention (week 7/prior to the post intervention clinical session). Adherence to the Mediterranean diet will be assessed using the Mediterranean Diet Adherence Screener Score (MEDAs) tool (Appendix H (iii)).

An ad libitum approach for each diet will be advised, based on previous literature (Papamiltiadous et al. 2016; Jacka et al. 2017; Itsiopoulos et al. 2011; Itsiopoulos et al. 2018; Ryan et al. 2013).

Participants will be instructed to maintain their habitual physical activity patterns during the intervention, with physical activity patterns monitored and evaluated weekly by informal individual support-orientated phone calls throughout the 8-week intervention. Food recall strategies will be adopted by researchers throughout these phone calls to monitor and evaluate dietary compliance.

[figure not shown]

Figure 1.0: A schematic overview of the 16-week research project. The consent/familiarisation session will take approximately one hour, and the clinical sessions will take approximately three hours each. All clinical sessions will involve questionnaires, body composition testing, blood pressure, and blood and stool sample collection. Buccal Swab/DNA testing will only occur at the baseline clinical session.

References:

4. Marques-Rocha, J. L., Milagro, F.I., Mansego, M.L., et al. (2016). "Expression of inflammation-related miRNAs in white blood cells from subjects with metabolic syndrome after 8 wk of following a Mediterranean diet-based weight loss program." *Nutrition*, 32(1): 48-55.

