5.8.1 Participant Commitment	Approximately 16 weeks. This includes the two 8-week nutritional intervention periods (Mediterranean Diet and control diet).
5.8.2 Project Duration	The project will commence as soon as ethics has been approved, and the proposed project conclusion date is December 31 st , 2020.
5.8.3 Participant Follow up	Not applicable.
5.8.4 Discontinuation criteria	Participants may be discontinued from participating in the case that they enrol meeting inclusion criteria; however, their circumstances change to meet exclusion criterion during participation. For example, a participant requiring antibiotic medication during their participation will be discontinued as this medication can exert an independent influence on the gut microbiota.

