5.9 Biological Sample Collection

5.9.1 What will be sampled and how?

Blood will be collected via IV catheterisation. Participants will rest in a supine position while a flexible 20-gauge Teflon catheter is inserted into an antecubital vein and attached to a three-way stopcock. This will allow for repetitive blood sampling during the oral glucose tolerance test (OGTT). The catheter will be kept patent by flushing it with isotonic saline after collection of each blood sample. Venous blood will be collected in EDTA, lithium heparin and serum-separating vacutainers. Blood samples will be collected on 3 clinical sessions. In the initial (baseline) clinical session and at a clinical session which immediately follows each of the 8-week dietary intervention periods (Mediterranean and control diet).

Oral Glucose Tolerance Test (OGTT): During each of the three clinical sessions, blood will be collected 4 times. A 20ml sample will be taken prior to glucose ingestion, and 20ml samples will be taken at 3 time points post ingestion (at 30 minutes, 60 minutes and 120 minutes). Thus, the maximum amount of blood taken per OGTT will be 80ml, with a total of 240ml taken throughout the research project. This compares with 500ml that is withdrawn during a standard donation at the blood bank.

Stool samples: Stool samples will be collected by participants. Participants will be provided with a stool collection kit (DNA Genotek OMNIgene-GUT Stool kit: <https://www.dnagenotek.com/us/products/collection-microbiome/omnigene-gut/OMR-200.html>) and related material. This includes a toilet collection hat, disposable gloves, collections spoons, a leak-proof primary receptacle with screw cap, leak-proof secondary receptacle with absorbent material and screw cap, padded envelope marked for mailing biological material and instructions for collecting/ mailing the specimen. An infographic of how

to collect the sample (Appendix I (ii)) and a short questionnaire about the collection time and date will be included in the collection kit.

Stool samples will be collected at three time points: within a week of the initial (baseline) clinical session, and at the end of each 8-week nutrition intervention (Mediterranean and control).

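### The diets switch at week 8 with no washout, and section 5.11 fixes an analysis with no diet, period or sequence term and no first-period comparison, so carry-over can bias the Mediterranean-versus-control contrast

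*Protocol*

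**What the plan says.** The design is stated in section 5.2: "The study will use a randomised, controlled, cross-over design". Section 5.3 sets the sequence of events. After the week-8 session, "The participant will then cross-over to the 8-week dietary intervention they have not yet completed". It continues: "Total duration of the combined dietary intervention period will be 16 weeks", and "A final (third) clinical session will be repeated at week 16". Section 5.8.1 puts the participant's commitment at about 16 weeks and adds: "This includes the two 8-week nutritional intervention periods". Section 5.9.1 places blood sampling at baseline and "at a clinical session which immediately follows each of the 8-week dietary intervention periods".

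The intervention is teaching. For the Mediterranean diet, "Each participant will receive a detailed sample Mediterranean meal plan, recipes, and education material to assist with adherence", together with a food hamper. The control diet is also taught, through food groups and serve sizes. Both diets are eaten ad libitum (sections 4.3 and 5.3).

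Aim (i) in section 4.7 compares the Mediterranean diet with habitual diet at baseline and with the control diet. Aims (ii) and (iii) ask whether genotype alters the response. Section 5.11 then fixes repeated-measures two-way ANOVA of genotype and time, pairwise comparisons over time, Tukey tests after a genotype-by-time interaction, and regression or ANCOVA for confounders of the genotype comparison. It does not name diet, period, sequence or a first-period comparison.

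**The concern.** In a two-period cross-over, each participant's control result is subtracted from the same participant's Mediterranean result. In the Mediterranean-first sequence the control result is taken at week 16, after eight weeks of Mediterranean teaching and no break. If some Mediterranean eating continues, the control value moves towards the Mediterranean value and the difference shrinks. Only the control-first sequence then gives the full difference.

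The analysis as worded offers no protection. Week 8 is a Mediterranean measurement in one sequence and a control measurement in the other, so a factor for time is not a factor for diet. If time is read generously as the three conditions (baseline, after Mediterranean, after control), the diet contrast is recovered, but order is still ignored and no carry-over-free estimate is reported beside it. At stake is the half of aim (i) that sets Mediterranean against control, and the genotype comparisons built on the same contrast.

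**Working it through.** **Washout.** 16 weeks − 8 − 8 = 0. Figure 1.0 is not shown, but the stated weeks leave no room for an interval.

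**Inputs from the protocol.** N = 120 after 20% inflation for attrition, 80% power for a medium effect (section 5.4), p < 0.05 (section 5.11). The figure of 120 cannot be reproduced, because no endpoint, SD, correlation, test or numerical effect is given, and the point does not depend on it. Undoing the inflation gives 120/1.2 = 100 completers; 20% dropout from 120 gives 120 × 0.8 = 96.

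**Assumptions.** 1:1 allocation to sequence, two-sided test, within-person correlation ρ of 0.5 to 0.7, effects in SD units. L is the fraction of the Mediterranean effect d still present at the end of the control period in the Mediterranean-first sequence. None of these values is in the protocol.

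**Bias.** Mean Mediterranean-minus-control difference:
- Mediterranean-first: d − Ld = d(1 − L)
- Control-first: d
- Average of the two sequences (period effects cancel): d(1 − L/2)

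Attenuation is L/2: 12.5% at L = 0.25, 25% at L = 0.5, 50% at L = 1. A simulation with true d = 0.5, 96 completers and ρ = 0.5 gave 0.4375, 0.3748 and 0.2513, against 0.4375, 0.375 and 0.25 from the formula. The first-period difference stayed at about 0.50 throughout.

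**Two-period power.** Noncentral t, N = 100, SE = √(2(1 − ρ)/100), which is 0.100 at ρ = 0.5 and 0.077 at ρ = 0.7:

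| True d | ρ | L = 0 | L = 0.25 | L = 0.5 | L = 1 |
|---|---|---|---|---|---|
| 0.25 | 0.5 | 70% | 58% | 46% | 24% |
| 0.25 | 0.7 | 89% | 80% | 67% | 36% |
| 0.5 | 0.5 | 99.9% | 99% | 96% | 70% |
| 0.5 | 0.7 | >99.9% | >99.9% | 99.8% | 89% |

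**First-period comparison.** 50 versus 50 at week 8, ANCOVA on week 0, SE = √((4/100)(1 − ρ²)), which is 0.173 at ρ = 0.5 and 0.143 at ρ = 0.7. Power is 30–41% for 0.25 SD, 40–55% for 0.3 SD and 82–93% for 0.5 SD. It is free of carry-over but less precise.

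**Gene-by-diet.** Take a diet effect of 0.75 in one genotype group and 0.25 in the other, a true difference of 0.50.
- L = 0.5 in both groups: 0.75 × 0.75 − 0.25 × 0.75 = 0.375
- L = 0.5 in the stronger responders only: 0.75 × 0.75 − 0.25 = 0.3125
- L = 0.5 in the weaker responders only: 0.75 − 0.25 × 0.75 = 0.5625

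The bias is therefore towards zero when persistence is similar, and can go either way when it differs. With 96 completers, equal genotype groups, ρ = 0.5 and common L, power for a difference of 0.50 is 69% at L = 0, 57% at L = 0.25 and 45% at L = 0.5.

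**Testing for carry-over afterwards.** Comparing participants' two-period totals between sequences, with 48 per sequence and ρ = 0.5, has about 11% power for a carry-over of 0.25 SD. A non-significant result would reassure nobody.

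**The case against.** The strongest objection is that a sensitivity analysis belongs in a statistical analysis plan, which may exist. That would hold if section 5.11 were silent. It names a specific model, and that model omits the factor that the cross-over was built to compare. The zero washout is also a protocol decision, so part of this objection falls.

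Other objections stand and limit the point:

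- **Direction.** A reader might infer that every contrast is pulled towards zero. The documents do not support that. The control diet is taught too and may persist into the Mediterranean period. If it pulls Mediterranean values back by the same fraction, attenuation doubles to L. If it leaves a larger lasting effect in the same direction as the Mediterranean effect, the sign of the bias reverses. Genotype-dependent persistence works either way, as shown above.
- **Time to fade.** Outcomes are read after eight weeks on the second diet, so short-lived physiological carry-over may have gone. Learned eating need not have.
- **Existing monitoring.** Section 5.3 plans weighed food records at weeks 4 and 7 of each diet and weekly calls with food recall. Section 5.8 has a food frequency questionnaire covering the previous eight weeks. Persistence can therefore be examined, although no analysis by sequence is stated.
- **Size.** At 0.5 SD, one common reading of a medium effect, the two-period analysis keeps high power even at L = 0.5. The serious losses are for smaller effects, where the first-period comparison is itself weak.
- **Week 8 as a baseline.** A reader might infer that week 8 will serve as a clean baseline for the second period. Section 5.11 does not say so, and sections 4.7, 5.3 and 5.9.1 use baseline only for the first session.
- **Hamper.** Continued use of hamper food during control is speculation. Section 4.3 describes the items as for use within the eight weeks.

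**Conclusion.** The point holds as a risk of bias that the stated analysis neither measures nor limits. The absence of washout and the absence of diet, period and sequence terms are matters of record. The size of the bias is not: it is L/2 of the diet effect under one-way Mediterranean persistence, and L must be assumed. Over L = 0.25 to 1 the Mediterranean-versus-control estimate loses 12.5% to 50%. Attenuation is the most plausible direction for that contrast but not a certain one, and for gene-by-diet contrasts it requires similar persistence across genotypes.

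It would go too far to conclude that a null result could not be interpreted. At L = 0.25 and ρ = 0.7, power for 0.25 SD is still 80%; Mediterranean versus baseline is untouched by Mediterranean carry-over; and the randomised first-period comparison exists in the data whether or not it is named. The change is worth making because it costs little and must be fixed before results are seen, but the design is not invalid without it.

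**What to change.** Keep the schedule. In section 5.11:

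1. Analyse the Mediterranean-versus-control contrast, and its interaction with genotype, in a model with diet, period and sequence terms. These terms put the contrast and the order of diets into the model; they do not remove carry-over, which is why the next step is needed.
2. For each primary outcome, pre-specify as a sensitivity analysis the randomised first-period comparison: Mediterranean versus control at week 8, ANCOVA on the week-0 value, reported beside the two-period estimate. Do not make a claim conditional on both estimates having the same direction; the first-period estimate is too imprecise for that.

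In sections 5.3 and 5.8, state that the Mediterranean adherence screener is given at weeks 0, 8 and 16 in both sequences, since its timing is not stated now. Report it by sequence with the food records already planned in each diet period, to show whether Mediterranean eating persists during control.

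Cost: analysis wording, and one or two extra short questionnaires at visits already planned. Downside: the first-period analysis has only about 30–41% power at 0.25 SD and 82–93% at 0.5 SD, and less for gene-by-diet, so it is supportive only.
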